Twenty subjects will be enrolled; the subjects will be randomly assigned to the experimental group (10 subjects) or to the control group (10 subjects) using a random number table. Subjects with the following conditions will be included: a) age >18 years, b) a single-unsplinted crown needed, c) a tooth must be in the area from the canine to the second molars, d) a CLP is required to fabricate a lithium disilicate crown. Exclusion criteria are as follows: a) uncontrolled hypertension, b) diabetes mellitus patients whose HbA1c level is 6.5% and above, c) subjects with a history of a long-term use of corticosteroid (> 6 months), d) subjects with a history of taking oral/IV bisphosphonates within the past 2 years, e) subjects taking anticoagulants, and f) smokers.

At the enrollment, if potential subjects are diabetic, the potential subjects are required to provide their A1c level verified by their primary care providers. The A1c level accepted needs to be within 3 months.

2) Clinical measurements:

A Williams probe (Hu-Friedy) will be used to obtain the level of gingival margin (GM), the width of keratinized gingiva (KG), and pocket depths (PDs).

The following measurements will be obtained at delivery of the crown.

- Gingival Margin (GM) will be measured from the cervical margin of the crown to the free gingival margin at the facial and lingual/palatal sites.
- The width of keratinized gingiva (KG) will be measured from the free gingival margin to the mucogingival junction (MGJ) at the midfacial and the midlingual surfaces. The MGJ will be identified by the color contrast between gingiva (pink) and mucosa (red).

The following measurements will be obtained at 12-month follow-up.

- Gingival Margin, b) The width of KG, c) Probing depths

3) Clinical photographs

will be taken at each appointment. Obtaining intraoral photographs is the standard way to compare before and after the treatments.

4) Radiographic measurements:

the radiographs will be exposed at baseline (the delivery of final prostheses; T_0) and 12-months follow-up (T_{12}). A blind evaluator will measure crestal bone loss from the crown margin to the most coronal aspect of the alveolar crest at the mesial and distal sides of the teeth on the bitewing radiographs. MiPACS® distal radiography system will be used to measure crestal bone level.

5) All procedures being performed for research purposes only

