All procedures being performed in this research (except obtaining signatures on the consent form) would need to be done for those patients regardless of their participation in this study.

The clinical photographs will be taken at the evaluation appointments and scanning with intraoral imaging will be obtained for the final impression. Obtaining the intraoral images is the standard way to compare before and after the treatments. All procedures described in the protocol are in accordance with the standard protocol for each treatment.

The final impression will be made with intraoral imaging (intraoral camera) in both groups (the experimental group and the control group).

Two diagnostic radiographs need to be made in both groups (the experimental and the control group) at delivery of crown and 12 months follow-up. No additional x-ray in the control group will be exposed. The fees for radiographs are included in the crown delivery and in periodic oral evaluation. Therefore, no additional fees will be charged.

The following procedures are research procedures.

1) If potential subjects are diabetic from medical history taking, the potential subjects are required to verify their HbA1c levels confirmed by their primary care providers. The A1c level accepted needs to be within 3 months.

2) Obtaining signatures on the consent form at screening visit in the experimental and the control group.

The PI and/or research team members will follow the protocol in the approved IRB application while we are obtaining signatures from the potential subject. The information will be given to the potential subject in the separate room. The potential subject will be encouraged to ask the PI and/or research team members any questions regarding this protocol.

3) The final impression made with intraoral imaging system at the surgery in the experimental group

This is a research procedure. Since intraoral imaging system allows us to take the impression without applying impression materials around teeth (in the mouth), the final impression could be made at the surgery without increasing any postoperative complications. No materials will be contacting the flap and the tooth. The PI and research team members are experienced dental providers and will carefully monitor subjects.

6) The duration of an individual participant's participation in the study

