The subjects may or may not get any benefits from participating in this study. They will receive the dental treatments that are indicated. The subjects assigned to the experimental group will get a crown earlier.

The results from this study would give a better prediction of the healing after CLPs and scientific supports for making the final impression at the surgery to expedite the delivery of final prostheses. Thus, this study will achieve a sustainable impact on the interdisciplinary field, both periodontics and restorative dentistry.

The surgical procedures and the dental restorative procedures in this study are in accordance with standard periodontal surgical procedures and standard restorative procedures. No more additional risk is encountered than at routine dental visits for periodontal surgery and restorative procedures. The PI and research team members will closely monitor all subjects in this study.

Participation is voluntary and the alternative is not to participate.

Follow-up

The study aims to follow participants up to 12 months after the delivery of the final crowns. Periodic oral evaluation, obtaining x-rays, and oral prophylaxis will be performed.

Data management and Statistical Analyses

1) Sample Size Determination

This study is the first clinical trial to determine the feasibility and safety of the proposed approach. Therefore, 10 subjects in each group are selected as a pilot study to clarify whether making the final impression at the surgery is acceptable or not.

2) Calibration for the Evaluator

SO will calibrate one investigator in terms of obtaining clinical parameters and radiographic crestal bone levels. SO and one investigator will measure GR, KG, PDs, BOP, and crestal bone levels and record Plaque Index separately for 10 patients. Pearson correlation coefficient (r) will be used to test the reliability.

3) Data Analysis: Descriptive statistics will be prepared for all outcome variables (mean \pm standard deviation). To test the null hypothesis of no difference in level of GM, PDs and CBLs at each time point between the experimental and control groups, independent t-tests will be conducted. The confidence interval (CI) of the treatment difference in crestal bone loss between the two groups will be evaluated against the non-inferiority margin (0.5 mm). A $p \leq 0.05$ will be considered significant.

Recruitment

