The research team members will recruit potential subjects through patients' screening, regular dental visits, and recall examinations. After the approval from IRB, the PI will present the brief summary of the study to the dental providers at the UMSOD. Dental providers who find a potential participant will introduce the study to a potential participant and will give the contact information to one of research team members upon patient's agreement. The PI and the research team members will ensure that all potential participants have a chance to talk and ask questions any time. The PI and the research team members will be sensitive to any signs of distress on the part of the participants. Individuals who refuse to participate will not be penalized in any way.

Eligibility Checklist

Inclusion/Exclusion Criteria (once the protocol is approved, this page must be copied, used as a checklist for screening subjects, signed by investigator, and inserted in research record for every subject screened):

Inclusion Criteria

Yes	No	Criteria	.
-----	----	----------	---

		age >18 years
		a single-unsplinted crown needed
		the tooth must be in the area from the canine to the second molar
		a CLP (crown lengthening procedure) is required to fabricate a crown

Exclusion Criteria

Yes	No	Criteria
		uncontrolled hypertension
		diabetes mellitus patients with whose HbA1c level is 6.5% and above
		subjects with a history of a long-term use of corticosteroid (> 6 months)
		subjects with a history of taking oral/IV bisphosphonates within the past 2 years
		smokers

Quality assurance

[name] and [name] perform quality monitoring. [name] is the principle investigator of the study. [name] is not a research team member. He has conducted several clinical trials at the UMSOD.

The final DSMB report is attached (Appendix 1).

Expected outcomes of the study

Making the final tooth preparation and the final impression at CLP will significantly reduce the time between the CLP and the delivery of the final crown and show comparable clinical outcomes.

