3) Filing out the consent form

If the potential participant decides to enroll, he/she will sign and enter the date on the current approved consent form. The PI or a co-investigator who obtains the consent will sign and date the informed consent form. The PI will keep the original informed consent form with the participant's study file in a locked cabinet at the room 4211. The participant will keep a hard copy of the original informed consent form.

4) HIPAA

During the informed consent process the participant will also sign the research HIPAA form. The PI or a co-investigator who conducts the informed consent process will explain to the participant that by signing the HIPAA form he/she authorizes his/her medical information to be shared with those parties listed on the form for the purposes of the research study. If the participant does not agree to sign the HIPAA form, he/she cannot

participate in the study. The original HIPAA form will be kept with the original consent form in the participant's study file.

Potential participants will receive research information in a separate private room at the UMSOD clinics to secure priva

Participants will be given ample time to read and assess the consent form. They will also be given as much time as needed to ask questions. The questions will be answered to their satisfaction.

If a participant presents for each appointment, a participant is implicitly willing to be in the study. Therefore, we will not consider for ongoing consent.

However, re-consenting may be required for various reasons including but not limited to cases where:

- 1) The original consent form was not properly executed (missing date, time, checkboxes, etc)
- 2) The study has been amended (i.e. changes in the study procedures affecting current participants)

Informed consent forms

The research informed consent form is attached (Appendix 3).

Appendix 1

Data and Safety Monitoring Report

Protocol Title: The Use of Intraoral Imaging at Clinical Crown Lengthening Procedures

Principal Investigator: [name]

Co-monitoring person: [name]

IRB#: HP-00073913

Date of the last IRB approval: 4/15/2020

The previous CR for the approved IRB protocol was obtained in April 2020. As of March 14, 2021, twenty-six subjects were enrolled and randomly assigned either to the experimental group or to the control group in this study.

Seven subjects were excluded from the study.

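### The mandatory signed eligibility checklist has no row for the anticoagulant exclusion listed in the Methodology section

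*Combined protocol and SAP*

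**What the plan says.** The combined protocol and SAP states the exclusion criteria twice.

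- **Methodology, 1) The Study population** gives a lettered list of six, a to f, ending with "e) subjects taking anticoagulants, and f) smokers".
- **Eligibility Checklist** (under Recruitment) sets the criteria out as Yes/No rows. The instruction above them reads: "this page must be copied, used as a checklist for screening subjects, signed by investigator, and inserted in research record for every subject screened". There are five exclusion rows.

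Three other places bear on the point.

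- **Methodology, 5)** (research procedures) describes a verification step for one exclusion only, the HbA1c check, which begins "If potential subjects are diabetic from medical history taking".
- **Data management and Statistical Analyses, 1) Sample Size Determination** gives the purpose of the trial: "This study is the first clinical trial to determine the feasibility and safety of the proposed approach".
- **Appendix 1**, the monitoring report, states that as of 14 March 2021 "twenty-six subjects were enrolled and randomly assigned", and that seven subjects were excluded from the study.

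**The concern.** The checklist is not an informal summary of the criteria. By its own instruction it is the signed eligibility record for each subject screened. If it omits a criterion, following the form exactly does not guarantee compliance with the protocol's own list, and the file cannot later show that the missing criterion was considered.

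The omitted criterion is relevant to this trial. Every subject has crown lengthening surgery, and Safety considerations lists bleeding after surgery first among the risks common to both groups. The stated aim includes safety, with 10 subjects planned per group, so a single ineligible subject would be 1/10 = 10% of a planned arm. A report that describes the enrolled population by the six Methodology criteria should be supportable from the records. For criterion e, the checklist gives no support.

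**Working it through.** No formula applies; the check is a line-by-line comparison of the two lists.

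| Methodology criterion | Subject matter | Checklist exclusion row |
|---|---|---|
| a | Hypertension | Row 1: "uncontrolled hypertension" |
| b | Diabetes, by HbA1c | Row 2: "diabetes mellitus patients with whose HbA1c level is 6.5% and above" |
| c | Long-term corticosteroids | Row 3: "subjects with a history of a long-term use of corticosteroid (> 6 months" |
| d | Bisphosphonates | Row 4 |
| e | Anticoagulants | None |
| f | Smoking | Row 5 |

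1. **Count.** Six criteria are listed, five have a row, and 6 − 5 = 1 is unmatched. The checklist adds no exclusion of its own.
2. **Order.** The five rows follow the Methodology order and skip only e. The bisphosphonate row is followed directly by the smoking row.
3. **Other checks.** In the available text, anticoagulants are mentioned only in the Methodology list. Criterion b is the only exclusion with a verification step of its own. Criteria a, c, d and f have none either, but each has a checklist row. Criterion e alone has neither. Methodology 5) mentions medical history taking, but only as the trigger for the HbA1c check.
4. **Could the row have been lost when the PDF was read?** The five rows run continuously, each with its own pair of boxes, with no gap, redaction or figure marker between rows 4 and 5. Loss of exactly one complete row is unlikely but cannot be fully excluded. The source page will settle it.
5. **Records concerned.** Appendix 1 gives 26 randomised, against 20 planned in Methodology 1). If the seven later exclusions were all among those 26, which is an assumption, 26 − 7 = 19 subjects remain. The text available gives neither the reasons for those exclusions nor the number screened. It also does not say which form version was used for each subject. The upper limit for enrolled records is therefore 26. The instruction also covers screened subjects who were not enrolled, whose number is not stated.

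**The case against.** The strongest reply is that this is a one-line clerical mismatch. The Methodology section states the exclusion without qualification, so the rule exists whether or not the form repeats it, and ordinary history taking may well identify a subject on anticoagulants. The planned analyses concern gingival margin, pocket depths and crestal bone level, with a 0.5 mm non-inferiority margin for crestal bone loss. A missing tick-box has no demonstrated effect on any of these, and the analysis paragraph defines no bleeding endpoint. Both groups have the same surgery, so there is no evident reason for a difference between arms. Enrolment has already passed its target, so correcting the form may have little prospective value.

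Much of this stands. No bias in the estimates is shown, no ineligible subject is known to have been enrolled, and any statement that no other check exists is limited to the text available.

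The reply does not remove the point. The protocol makes this page the mandatory eligibility record, so the two lists can give different answers for the same subject, and a correctly completed form does not reveal the difference. That enrolment is advanced affects the remedy: it moves the emphasis from the form to the records. The seven reported exclusions do not help, because the available text does not say why they were made.

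**Conclusion.** The inconsistency is real. Five of the six Methodology exclusions have a checklist row; the anticoagulant criterion has none, and no separate check of it is described. Up to 26 enrolled records are open to question on this one criterion. The number of subjects affected is unknown and may be zero, and the documents give no basis for quantifying harm or bias.

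The conclusion rests on the checklist having been read completely from the source page, and on no check of this criterion appearing in parts of the document that were not available. It should be corrected: the defect is in a mandatory form relevant to safety and the correction is cheap, although its consequence is unproven.

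**What to change.** 1. Confirm on the source page that the row is absent.
2. Make the exclusion lists in Methodology 1) and the Eligibility Checklist identical. The sponsor decides which list is intended.
3. For subjects already screened on the five-row form, including up to 26 enrolled, review the medical history for criterion e as written in the Methodology section. Record the result and document any deviation. This is the main remedy, because randomisation has already taken place.
4. In the trial report, state how criterion e was ascertained and how many subjects, if any, did not meet the eligibility list as finally reconciled.

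The cost is one line in one of the two lists and a review of at most 26 enrolled records, plus any forms held for subjects screened but not enrolled. Sample size and planned analyses do not change.
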